### 5.2 Exclusion Criteria

1. Women who are pregnant, breastfeeding, or planning to become pregnant during the trial
2. Blood donation during or within 30 days of the last study visit
3. Taking any specific energy supplements or vitamins at least 1 month prior to and during the trial as assessed by the QI
4. Unstable weight for the last 2 months prior to the study assessed case by case by QI
5. Individuals on a low protein diet
6. Excessive consumption of alcohol equivalent to >2 alcoholic drinks/day
7. Use of marijuana assessed case by case by QI
8. Known allergy to the test material's active or inactive ingredients
9. Clinically significant abnormal Physical Examination results at screening

Protocol 18PEHH: A proof-of-concept study to evaluate the efficacy of Salmon Protein Hydrolysate Powder on energy increase and anti-inflammatory modulation in healthy males and females.

10. Participation in clinical trials in the past 30 days
11. Cognitively impaired and/or unable to give informed consent
12. current cardiovascular disorders or uncontrolled blood pressure will be assessed by QI)
13. Verbal confirmation of history of or current diagnosis of bleeding/blood disorder
14. Verbal confirmation of Type I or Type II diabetes
15. Verbal confirmation of kidney disease
16. Verbal confirmation of history of liver disease
17. Anemia based on hemoglobin and hematocrit at screening
18. Thyroid disease assessed case by case by QI (5.3.1)
19. Iron Supplementation (5.3.1)
20. Mood stabilizers assessed case by case by QI (5.3.1)
21. Energy boosting supplements (5.3.2)
22. Individuals on workout supplements (5.3.2)
23. Habitual users of energy drinks
24. Melatonin supplementation assessed case by case by QI (5.3.2)
25. Autoimmune disease or if immune-compromised (i.e. HIV positive, use of anti-rejection medication, rheumatoid arthritis, Hepatitis B/C positive)
26. Surgical procedures which may impact the study outcomes within the past 3 months to be assessed by the QI
27. Cancer, except skin cancers completely excised with no chemotherapy or radiation with a follow up that is negative. Volunteers with cancer in full remission will be assessed by the QI for inclusion.
28. Presence or history of neurological disorders or significant psychiatric illness as assessed by QI
29. Any other condition, in the QI's opinion, which may adversely affect the participant's ability to complete the study or its measures or which may pose significant risk to the participant

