#### **Secondary outcomes:**

1. Change from baseline to Day 128 in Red Blood Cell (RBC) count, RBC indices (MCV, MCH, MCHC), hematocrit, and Red Cell Distribution Width (RDW) after supplementation with Salmon Protein Hydrolysate Powder (ProGo®)
2. Change from baseline to Day 128 in Hemoglobin (Hb) after supplementation with Salmon Protein Hydrolysate Powder (ProGo®)
3. Change from baseline to Day 128 in relative expression of 84 stress genes (Section 14.5) as evaluated by oxidative stress-related gene RT Profiler PCR array after supplementation with Salmon Protein Hydrolysate Powder (ProGo®)
4. Change from baseline to Day 128 in total Reactive Oxygen Species/Reactive Nitrogen Species free radical activity assessed by ROS/RNS assay after supplementation with Salmon Protein Hydrolysate Powder (ProGo®)
5. Change from baseline to Day 128 in levels of human inflammatory cytokines (IL-1RA, IL-4, IL-6, IL-10, IL-11, IL-13 and TGF- $\beta$ ) as measured by the Multi-Analyte ELISArray after supplementation with Salmon Protein Hydrolysate Powder (ProGo®)
6. Change from baseline to Day 128 in glycated hemoglobin (HbA1c) and fasting glucose after supplementation with Salmon Protein Hydrolysate Powder (ProGo®)
7. Change in score of the Hair, Nails, and Skin Self-Assessment Questionnaire after 128-day supplementation with Salmon Protein Hydrolysate Powder (ProGo®)

[figure not shown]

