### 7.4 Visit 3; End-of-Study; Week 18 (Day 128 ± 3)

Participants will return to the clinic for Visit 3 assessments with any unused investigational product and completed study diaries if any. An 8-hour fasting period is required for this visit.

Visit 3 assessments include:

1. Return unused investigational product in the original packaging and remnants and calculation of compliance by counting the returned unused investigational product
2. Ensure that study apps have been reviewed
3. Collect and review study diaries if applicable
4. Weight measurement (BMI calculation)
5. Waist and hip circumference measurements

Protocol 18PEHH: A proof-of-concept study to evaluate the efficacy of Salmon Protein Hydrolysate Powder on energy increase and anti-inflammatory modulation in healthy males and females.

6. Seated resting blood pressure and heart rate measurements
7. Collect blood sample for CBC
8. Collect blood samples for future analysis (Section 7.5.8):
  - Oxidative stress-related gene expression (Sections 7.5.8.1 and 14.5)
  - Total ROS/RNS free radical activity (Section 7.5.8.2)
  - Human inflammatory cytokine levels (Section 7.5.8.3)
9. Collect blood samples for HbA1c and fasting glucose
10. Complete Vitality and Quality of Life Questionnaire (Section 14.2)
11. Complete Hair, Nails, and Skin Self-Assessment Questionnaire (Section 14.4)
12. Physical Examination (excludes genital and rectal examination)
13. Review concomitant therapies and adverse events

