## 7.6 Laboratory Analyses

Blood samples will be drawn from the participants at screening (Visit 1), baseline (visit 2), and the end of Study (Visit 3) as indicated in the schedule of assessments. Blood draws will be performed from a participant's arm via venipuncture. See Section 11.3 for potential risks associated with venipuncture.

Protection of participant confidentiality will extend to all data generated from the assaying of these samples. These samples will be alphanumerically coded and the persons performing the analysis will not be aware of the subject's identity.

At screening (Visit 1), 4 mL of whole blood will be collected in:

1. 1 x 4 mL EDTA vacutainer tube to generate plasma for:
  - a. CBC (1 tube)

At baseline (Visit 2), 23 mL of 8 hour fasting whole blood will be collected in:

1. 1 x 4 mL EDTA vacutainer tube to generate plasma for:
  - a. HbA1c (1 tube)
2. 1 x 4 mL EDTA vacutainer tube for whole blood for:
  - a. Future analysis - Gene expression analysis (1 tube)
3. 3 x 5 mL SST vacutainer tube to generate serum for:
  - a. Future Analysis - ROS/RNS and Inflammatory Cytokines (2 tubes)
  - b. Fasting Glucose (1 tube)

At the end of the study (Visit 3), 27 mL of 8 hour fasting whole blood will be collected in:

1. 2 x 4 mL EDTA vacutainer tube to generate plasma for:
  - a. CBC (1 tube)
  - b. HbA1c (1 tube)
2. 1 x 4 mL EDTA vacutainer tube for whole blood for:
  - a. Future analysis - Gene expression analysis (1 tube)
3. 3 x 5 mL SST vacutainer tube to generate serum for:
  - a. Future Analysis - ROS/RNS and Inflammatory Cytokines (2 tubes)
  - b. Fasting Glucose (1 tube)

The total blood volume collection for the laboratory assessments listed above will be approximately 54 mL, over the period from screening to end of study (approximately 128 days). At any study visit, blood loss per volunteer is not expected to exceed 27 mL. Additional blood samples may be collected during the course of the study in order to perform or repeat laboratory tests outlined in the Schedule of Assessments if needed.

The central laboratory, Life Labs, London Ontario, will be used in this study to measure CBC, HbA1c, and fasting glucose.

Blood collected for future analysis will be shipped to the sponsor.

Urine pregnancy test will be performed at the KGK Science clinic site.

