## 14 APPENDICES

### 14.1 Appendix I - Schedule of Assessments

#### Schedule of Assessments (N=20)

	Visit 1 Screening	Visit 2 Baseline Day 0	Visit 3 Week 18 Day 128
Informed consent	X		
Review inclusion/exclusion criteria	X	X	
Review medical history	X		
Review concomitant therapies	X	X	X
Height*, weight, heart rate, blood pressure, waist & hip circumference	X	X	X
Urine pregnancy test	X	X	
Physical examination	X		X
Complete Blood Count	X		X
Product Tolerance Questionnaire	X		
DNA – buccal cells**		X	
Future analysis blood draws** (oxidative stress-related gene expression, total ROS/RNS free radical activity, human inflammatory cytokine levels)		X	X
HbA1c and Fasting plasma glucose		X	X
Quality of Life Questionnaire		X	X
Hair, Nails, and Skin Self-Assessment Questionnaire		X	X
IP dispensed		X	
IP returned			X
Study diary dispensed		X	
Study diary returned			X
Compliance calculated			X
Adverse events pre-and post-emergent		X	X

\* only measured at Visit 1

\*\*KGK to draw, process and store blood for shipment to lab. Lab costs and shipment costs to be covered by Sponsor.

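### The blood-donation exclusion has no look-back before the screening CBC, the only pre-product value for the secondary Hb and red-cell outcomes

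*Combined protocol and SAP*

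**What the plan says.** Section 5.2, exclusion 2, is the only criterion that mentions donation: "Blood donation during or within 30 days of the last study visit". No inclusion criterion in Section 5.1 and no listed screening step in Section 7.1 asks about earlier donation.

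The outcomes that depend on it are secondary outcomes 1 and 2 in Section 3: "Change from baseline to Day 128 in Red Blood Cell (RBC) count, RBC indices (MCV, MCH, MCHC), hematocrit, and Red Cell Distribution Width (RDW") and "Change from baseline to Day 128 in Hemoglobin (Hb) after supplementation".

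The sampling that feeds them is as follows.

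- **Visit 1.** Section 7.6 states "At screening (Visit 1), 4 mL of whole blood will be collected in" a single EDTA tube, which is for the CBC.
- **Visit 2 (Day 0).** Section 7.6 states "At baseline (Visit 2), 23 mL of 8 hour fasting whole blood will be collected in" tubes for HbA1c, gene expression, ROS/RNS, cytokines and glucose. None is for a CBC.
- **Visit 3.** Section 7.4 lists "Collect blood sample for CBC".
- **Appendix I.** The "Complete Blood Count" row is marked at Visits 1 and 3 only.

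Section 4 describes one open-label arm. Section 9.3 tests whether mean change differs from zero, by paired t-test or Wilcoxon signed-rank test.

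**The concern.** Donation temporarily lowers Hb, RBC count and hematocrit. A volunteer who gave blood shortly before Visit 1, and whose values stayed above whatever the site calls anemia, meets the criteria as written. That person's only pre-product CBC is then depressed, and no second pre-product CBC exists to show it.

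The final CBC comes roughly four to six months later, so there is time to recover. The recovery goes in the direction the plan hopes to see: the Introduction cites raised red cells and hemoglobin with this product. With no control arm, and change tested against zero, the analysis cannot separate recovery from a product effect. Nor could the problem be examined afterwards, because no listed step records the donation date.

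Other entry criteria in Section 5.2 do look back from entry: 1 month for energy supplements or vitamins, 2 months for unstable weight, 30 days for other trials and 3 months for surgery. Donation, which acts directly on the CBC outcomes, has no such period.

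**Working it through.** **1. The plan's own figure.** Section 9.1 gives 16 completers, 20% attrition and 20 enrolled: 16 / (1 − 0.20) = 20. This reproduces. There is no power calculation, and no SD, effect size or alpha is stated.

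**2. Time between the two CBCs.** Visit 1 falls between Day −45 and Day −1, and Visit 3 on Day 128 ± 3.
- Shortest: 1 + 125 = 126 days.
- Longest: 45 + 131 = 176 days.

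**3. Inputs for size.** From the plan: n = 16 completers and a paired test of change against zero. Assumed, because the documents do not say: k recent donors among the 16; Hb recovery d of 0.5 to 1.5 g/dL per donor by Visit 3; SD of Hb change 0.6 g/dL (0.5 to 0.7 as a check); two-sided 5% test; no product effect.

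**4. Shift in mean Hb change.** Shift = k × d / n.
- k = 1: 0.5/16 = 0.03 to 1.5/16 = 0.09 g/dL.
- k = 2: 1.0/16 = 0.06 to 3.0/16 = 0.19 g/dL.
- k = 4: 2.0/16 = 0.13 to 6.0/16 = 0.38 g/dL.

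For scale, the mean change needed for p < 0.05 is t(0.975, 15 df) × SD / √16 = 2.131 × 0.6 / 4 = 0.32 g/dL.

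**5. Rejection rate with no product effect.** Simulated paired t-test, n = 16, SD 0.6, 400,000 runs per cell, with d added to k of the 16 changes:

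| Recent donors | Shift (g/dL) | Two-sided rejection | False finding of an increase |
|---|---|---|---|
| 0 | 0 | 5.0% | 2.5% |
| 1 | 0.03 to 0.09 | 4.7% to 5.0% | 3.6% to 4.5% |
| 2 | 0.06 to 0.19 | 5.8% to 8.5% | 5.1% to 8.5% |
| 4 | 0.13 to 0.38 | 9.8% to 27.7% | 9.6% to 27.7% |

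One donor hardly moves the two-sided rate because a single large change also inflates the SD in the denominator. It does move the errors towards the favorable side.

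**6. Sensitivity to the SD.** With SD 0.5 to 0.7 g/dL, one donor gives 4.4% to 5.0%, two give 5.6% to 8.6% and four give 8.7% to 31.7% (two-sided). The pattern is the same.

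Only Hb is quantified. RBC count and hematocrit should follow the same logic; the size and direction for the indices and RDW were not worked out.

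**The case against.** The best case against the point has four parts.

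- **The wording is broader than it first looks.** A reader might infer that the exclusion is tied only to the last visit and leaves in-study donation open. The text does not support that: the word *during* most naturally covers the study period. What remains open is the time before Visit 1.
- **Other criteria narrow the route.** Exclusion 17 removes volunteers judged anemic at screening, which limits how far an enrolled donor's starting value can be depressed. Inclusion 8 requires good health on medical history and laboratory results, and exclusion 29 gives the investigator discretion. These make several donors with large recoveries less plausible. They do not close the gap: exclusion 17 states no threshold, non-anemic donors pass, and discretion depends on learning of a donation that no listed step asks about.
- **The numbers are small unless several donors enrol.** This stands. One donor in 16 has almost no effect on the two-sided error rate, and nothing in the documents suggests that two or four would enrol.
- **The consequence is limited.** This also stands. Hb and the red-cell measures are secondary. A reader might infer that the energy result is biased too, but the primary outcome is a questionnaire score and nothing in the documents shows that it would be affected. Without a control arm, Hb change is open to other time-related drift anyway, so closing this gap would not by itself make the change attributable to the product.

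A further tempting inference is that the plan's 30 days, moved to the front of the study, would be enough. The plan uses that interval around the last visit and does not present it as a recovery period. If recovery takes months, someone who donated 31 days before Visit 1 would still be recovering.

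**Conclusion.** The gap holds, at minor severity. Exclusion 2 has no look-back before the CBC that serves as the only pre-product value for secondary outcomes 1 and 2, and the design cannot separate post-donation recovery from a product effect. Under the assumed recovery and an SD of 0.6 g/dL, the effect runs from negligible with one recent donor (two-sided error about 5%) through slight with two (about 6% to 9%) to material only in the extreme case of four among 16 (about 10% to 28%). The number of donors, the recovery and the SD are all assumptions. The existence of the gap does not depend on them; its size does.

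**What to change.** Reword exclusion 2 so that it excludes blood donation within a stated period before the Visit 1 CBC, as well as from then through Visit 3. The sponsor should set that period and justify it as long enough for Hb and RBC to recover; the existing 30 days is not shown to be enough. Any period after Visit 3 has no bearing on the CBC outcomes and needs its own reason if it is kept.

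Add one question to the Section 7.1 screening list that records the date of last donation. State in Section 9.3 that the Hb and red-cell results will also be shown without recent donors, if any are enrolled.

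The cost is one phrase, one screening question and one sentence in the analysis plan. The target of 16 completers from 20 enrolled is unchanged. The downside is that some recent donors will be screened later or excluded.

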### **5.3 Concomitant Medications and Washout Periods**

Participants who are currently taking any prescribed medications must agree to maintain their current method and dosing regimen during the course of the study unless recommended by their physician.

#### **5.3.1 Prescribed Medications**

Participants on the following concurrent prescribed medications/treatments will be assessed by the QI:

1. Thyroid medications to be evaluated case by case by QI
2. Mood stabilizers to be evaluated case by case by QI
3. Iron supplementation

#### **5.3.2 Over-the-counter Medications, Supplements, and Foods/Drinks**

Volunteers who are currently consuming the following supplements will not be allowed to participate unless willing to undergo a 2-week washout:

1. Energy boosting supplements
2. Workout supplements
3. Melatonin supplements to be evaluated case by case by QI

Protocol 18PEHH: A proof-of-concept study to evaluate the efficacy of Salmon Protein Hydrolysate Powder on energy increase and anti-inflammatory modulation in healthy males and females.

### **5.3.3 Rescue Medications**

Not applicable.

## **5.4 Premature/Discontinuation Criteria**

### **Personal reasons**

As stated in the Informed Consent Form, a participant may withdraw from the study for any reason at any time.

### **Removal by Qualified Investigator**

Participant discontinuation should be considered at the discretion of the qualified investigator. The circumstances of any discontinuation have to be documented in detail in the participant file and final report. If possible, the evaluations planned for the end of treatment will be carried out at the time when the participant is withdrawn from the study. A participant leaving the study prematurely will NOT be replaced by another. It is understood by all concerned that an excessive rate of withdrawals can render the study uninterpretable; therefore, unnecessary withdrawal of participants should be avoided.

Criteria for removal of participants from the study will include:

#### *Clinical reasons*

A participant may be withdrawn from the study if, in the opinion of the qualified investigator, it is not in the participant's best interest to continue. Any participant who experiences a serious adverse event (SAE) may be withdrawn from the trial at the discretion of the qualified investigator. A participant will also be withdrawn due to adverse events causing clinically significant illness or the need for prohibited medication(s) during the trial.

#### *Protocol violation*

Any participant found to have entered this study in violation of the protocol will be discontinued from the study at the discretion of the qualified investigator. This will include any participant found to have been inappropriately enrolled (did not meet eligibility criteria). Participant non-compliance includes not showing up for study visits, not taking the investigational product as directed, or refusing to undergo study visit procedures. Participants who are found to be taking prohibited medications or supplements without the knowledge of the qualified investigator will also be withdrawn. Any major protocol deviations (i.e., those that increase the risk to participants and/or compromise the integrity of the study or its results) will result in participant discontinuation.

Protocol 18PEHH: A proof-of-concept study to evaluate the efficacy of Salmon Protein Hydrolysate Powder on energy increase and anti-inflammatory modulation in healthy males and females.

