## 7.5.9 Compliance

Compliance will be assessed by counting the returned unused study product at each visit. Compliance is calculated by determining the number of dosage units taken divided by the number of dosage units expected to have been taken multiplied by 100.

$$\frac{\text{number of dosage units taken}}{\text{number of dosage units expected to have been taken}} \times 100\%$$

In the event of a discrepancy between the information in the treatment diary and the amount of study product returned, use will be based on the product returned unless an explanation for loss of product has been provided. Participants found to have a compliance of  $<80\%$  or  $>120\%$  will be counseled.

Protocol 18PEHH: A proof-of-concept study to evaluate the efficacy of Salmon Protein Hydrolysate Powder on energy increase and anti-inflammatory modulation in healthy males and females.

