### 9.2 Analysis Plan

1. The **Safety Population** will consist of all participants who received any amount of product, and whom any safety information is available.
2. The **Intent-to-Treat (ITT) Population** consists of all participants who received product and whom any efficacy information is available.
3. The **Per Protocol (PP) Population** consists of all participants who consumed at least 80% of treatment doses, do not have any major protocol violations, and complete all study visits and procedures connected with measurement of the primary variable.

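### Section 5.4 removes major deviators and undisclosed users of prohibited products from the study without securing their Day 128 data, so the ITT analysis carries little information on them

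*Combined protocol and SAP*

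**What the plan says.** **Removal.** Section 5.4 opens by leaving discontinuation to the investigator's judgement, warns against needless withdrawals and rules out replacement. It then introduces its list with "Criteria for removal of participants from the study will include". Under the Protocol violation heading the language is firmer: major deviations (those that raise risk for people enrolled, or that "compromise the integrity of the study or its results) will result in participant discontinuation". People using prohibited medications or supplements without the investigator's knowledge are also withdrawn.

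**Evaluation on leaving.** The same section adds: "If possible, the evaluations planned for the end of treatment will be carried out at the time when the participant is withdrawn from the study".

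**Non-adherence.** Section 5.4 states: "Participant non-compliance includes not showing up for study visits, not taking the investigational product as directed, or refusing to undergo study visit procedures". That sentence gives no consequence. Section 7.5.9 says that participants with compliance below 80% or above 120% "will be counseled", and nothing more.

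**Retention elsewhere.** Section 8.2.2 covers two groups: those who withdraw on their own initiative and those with clinically significant unexplained laboratory abnormalities. Both stop treatment but stay in the study and attend the remaining visits.

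**Analysis.** In Section 9.2 the ITT population "consists of all participants who received product and whom any efficacy information is available". The PP population needs at least 80% of doses, no major violation, and completion of the visits and procedures for the primary variable. Section 9.3 analyses both sets, fills missing efficacy values by LOCF and does not impute safety values. Section 4 places outcome assessments at baseline and Day 128.

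**The concern.** An ITT analysis presented beside a PP analysis should show what happened to everyone who started, including those who departed from the protocol. That requires their outcomes to be measured. Here a deviation can itself end follow-up, so the rule creates the missing data that LOCF must then fill.

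The primary outcome is a self-reported questionnaire in an open-label, single-arm study, so whether a participant keeps to the protocol may plausibly be related to how that person feels. That link is a possibility, not something the documents establish. At 20 participants, each lost observation is 5% of the sample and is not replaced.

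Safety is affected as well. The Schedule of Assessments has a complete blood count at screening and Visit 3 only. Someone removed without an evaluation at withdrawal has no scheduled blood count after starting the product.

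**Working it through.** **1. The plan's own figure.** Section 9.1 asks for 16 completers and allows 20% attrition: 16 / (1 - 0.20) = 20. This reproduces. The section gives no effect size, SD or power, so the effect figures below are assumptions.

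**2. What happens to a removed participant.** With a baseline questionnaire, the person plausibly meets the ITT definition, which does not ask for Day 128 data. There are then two cases:
- An evaluation at withdrawal takes place. The ITT analysis uses a value from a shorter exposure.
- No evaluation takes place. The only earlier value is baseline, so LOCF sets the change to 0.

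In neither case is there an observed Day 128 value.

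**3. Effect on the mean.** Assume *k* of 20 are removed with no early evaluation, completers change by *d* = 0.5 SD on average, and the removed would have changed by *c*.

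- LOCF ITT mean = (20 - *k*) × *d* / 20
- True mean = [(20 - *k*) × *d* + *k* × *c*] / 20
- Difference (LOCF minus true) = -*k* × *c* / 20

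| *k* | LOCF ITT mean | True, *c* = -0.5 | True, *c* = 0 | True, *c* = +0.5 |
|---|---|---|---|---|
| 1 | 0.475 | 0.45 | 0.475 | 0.50 |
| 2 | 0.45 | 0.40 | 0.45 | 0.50 |
| 4 | 0.40 | 0.30 | 0.40 | 0.50 |

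For *k* = 4: LOCF gives 16 × 0.5 / 20 = 0.40. The true means are (8 - 2)/20 = 0.30, 8/20 = 0.40 and (8 + 2)/20 = 0.50. LOCF is therefore 33% too high (0.40/0.30 = 1.33), exact, or 20% too low (0.40/0.50 = 0.80).

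**4. Effect on the test.** Take *k* = 4, completer SD of change 1, the 16 completers as the PP set, and a two-sided paired t-test (the plan states neither alpha nor sidedness).

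- PP: t = *d* × √16
- ITT: mean = 0.8*d*; SD = √{[15 + 16 × (0.2*d*)² + 4 × (0.8*d*)²] / 19}; t = mean / (SD/√20)

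| *d* | PP t | PP p | ITT t | ITT p |
|---|---|---|---|---|
| 0.5 | 2.00 | 0.0639 | 1.96 | 0.0646 |
| 0.75 | 3.00 | 0.0090 | 2.85 | 0.0102 |
| 1.0 | 4.00 | 0.0012 | 3.66 | 0.0017 |

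A signed-rank test that discards zero changes gives the same p-value as leaving the four out. The ITT test thus adds almost nothing to the PP test on these participants.

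**5. Whether non-adherence takes this route.** Product is dispensed at Visit 2 and returned and counted at Visit 3, when the Day 128 outcomes are also collected. Non-adherence found by count therefore cannot by itself cost the Day 128 data. Earlier detection would have to come from the Week 6 and 12 calls, the diary or the app, and no section says that removal follows from these.

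**The case against.** The strongest reply is that the plan already limits the damage. Section 5.4 asks for the end-of-treatment evaluations at withdrawal, gives the investigator discretion and discourages unnecessary withdrawals. Removed participants stay in the ITT set, and this is a 20-person proof-of-concept study. Much of this stands. But the evaluation is conditional and gives at best an early value. The discretion sits uneasily with the mandatory wording for major deviations. Section 8.2.2 shows that the protocol can keep people in the study after they stop product.

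A reader might infer more than the documents support:

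- **That the ITT set shrinks to the PP set.** It does not. Membership can remain 20, and with four removed the LOCF ITT mean is 0.80 of the PP mean. Only the p-values come close.
- **That the ITT effect is overstated by 25% or 67%.** Those figures (0.50/0.40 and 0.50/0.30) set the completers' mean against the true mean. The planned ITT estimate under LOCF is 0.40 SD, so the corresponding errors are 0% and 33%, and an understatement is equally possible. The larger figures would apply only if the undefined qualifier on which missing values are imputed in Section 9.3 were read to leave these participants out.
- **That 5.4 and 7.5.9 flatly contradict each other on non-adherence.** Section 5.4 names it without a consequence and 7.5.9 prescribes counselling. Whether it counts as a major deviation is left open, which is an ambiguity.

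**Conclusion.** The point holds in a limited form. As written, Section 5.4 takes major deviators and undisclosed users of prohibited products out of the study and does not secure their Day 128 outcomes. The ITT analysis then holds an early value or a baseline-carried zero for them, and non-imputed safety data may be lost.

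Under the assumptions of 4 of 20 removed, no early evaluation and completers at +0.5 SD, the ITT mean could be 0.10 SD too high or too low, or correct, for changes of -0.5 to +0.5 SD among the removed. With one removed the error is at most 0.025 SD over the same range. The documents give no basis for the number removed or for their outcomes, so neither the direction nor the size of the bias can be stated as fact. For non-adherence alone, Day 128 data are at risk only if it is detected before Visit 3 and treated as grounds for removal. This is a cheap improvement worth making; it does not invalidate the design.

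**What to change.** Reconcile Sections 5.4, 7.5.9 and 8.2.2, with these elements:

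1. Separate stopping product from leaving the study. The rules on stopping product remain the sponsor's to set.
2. State that a protocol deviation does not by itself end data collection. The Day 128 questionnaire, bloods and adverse-event review are obtained from everyone who still consents.
3. Say whether non-adherence is a major deviation, and how the discretionary and mandatory wording in 5.4 fit together.
4. In Section 9.3, state that observed Day 128 values are used in the ITT analysis whatever the deviation. Deviators are handled through the existing PP definition in 9.2.

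The cost is protocol wording and a small follow-up effort for participants who are off product. The Day 128 visit is already in the schedule for all 20.
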